#### Within 7 Days Prior to First Dose of BAY 1163877

- Update of inclusion / exclusion criteria
- Review of baseline toxicities
- Update of concomitant therapy
- Body weight and height, calculation of BMI
- Vital signs (body temperature, respiration rate, blood pressure, heart rate)
- Blood and urine collection for safety laboratory tests. In case of abnormal results caused by intercurrent diseases, short-term treatable conditions or other temporary health disorders, the investigator may decide to repeat the respective screening parameter(s). As a rule, up to 2 repetitions are acceptable, for details see Table 16-4
- Only for females of childbearing potential: Urine pregnancy test (the negative

-

<sup>56 Part 3 - Safety cohort - was added by Amendment 7, see section 15.6.2.20

 Part 3 was added by Amendment 7, see section 15.6.2.20

<sup>58 Amended for clarification by Amendment 7, see section 15.6.2.20

No. BAY 1163877 / 16443

17 Oct 2018 Version 8.0 Page: 73 of 395

result must be documented before start of study drug treatment)

- Calculation of eGFR (see Section 16.9)
- Documentation of lesion(s) according to RECIST v1.1
- Adverse events before start of treatment (results of physical examination)
- Only for subjects in Part 3: peripheral blood sample collection for determination of cytokine levels in serum. 

#### 9.1.2.2 Randomization

Not applicable (see Section 8.3).

#### 9.1.2.3 Treatment - amended

For subjects in the "tablet bridging cohort" and "food effect assessment", the treatment phase starts on Cycle 1, Day -3, followed by Cycle 1 (21 days) and a variable number of subsequent Cycles (each of 21 days duration) with no break between Cycles.

For all other subjects, the treatment phase comprises Cycle 1 (21 days) and a variable number of subsequent Cycles (each of 21 days duration) with no break between Cycles.

There will be both visits and possible overnight stays at the study site.

Patients with an estimated GFR in the range 30 mL/ min to 60 mL/min should be carefully monitored for signs of increased toxicity.

#### 9.1.2.3.1 Cycle 1- amended

For "tablet bridging cohort" or "food effect assessment" only:

#### Day -3 to Day -1 (possible overnight stay)

#### **Day -3**

- Update of concomitant therapy
- Physical examination
- Ask subject for changes in vision
- Cardiovascular assessment (BP and HR)
- Measurement of body temperature and body weight
- Triplicate 12-lead ECG readings (see Section 9.5.3.4).

<sup>59 Part 3 was added by Amendment 7, see section 15.6.2.20

 Added by Amendment 6, see section 15.6.2.21

No. BAY 1163877 / 16443

17 Oct 2018 Version 8.0 Page: 74 of 395

- ECOG performance status
- Blood and urine collection for safety laboratory tests (repetitions for controls may be necessary), for details see Table 16-4
- Calculation of eGFR (see Section 16.9)
- Single oral administration of BAY 1163877 tablet formulation ("tablet bridging cohort" only)
- Single oral administration of BAY 1163877 tablet formulation immediately after consumption of high-fat, high-calorie meal as specified in Section 8.4.2.2.1 ("food effect assessment" only)
- PK sampling
- Toxicities / AE assessment and recording (if applicable)

#### Day -2

- No administration of BAY 1163877 ("drug-free day")
- Update of concomitant therapy
- Physical examination
- Ask subject for changes in vision
- Cardiovascular assessment (BP and HR)
- Measurement of body temperature
- Triplicate ECG readings (see Section 9.5.3.4)
- ECOG performance status
- PK sampling
- Toxicities / AE assessment and recording (if applicable)

#### Day -1

- No administration of BAY 1163877 ("drug-free day")
- Update of concomitant therapy
- Physical examination
- Ask subject for changes in vision
- Cardiovascular assessment (BP and HR)
- Measurement of body temperature
- ECOG performance status
- PK sampling

No. BAY 1163877 / 16443

17 Oct 2018 Version 8.0 Page: 75 of 395

Toxicities / AE assessment and recording (if applicable)

#### Days 1-3 (possible overnight stay)

#### Day 1

- Update of concomitant therapy
- Physical examination
- Ask subject for changes in vision
- Cardiovascular assessment (BP and HR)
- Measurement of body temperature and body weight (measurement of weight not required for subjects in the "tablet bridging cohort" and for subjects with "food effect assessment")
- Single 12-lead ECG reading (see Section 9.5.3.4)
- ECOG performance status
- Blood and urine collection for safety laboratory tests (repetitions for controls may be necessary), for details see Section 16.2.
- Calculation of eGFR (see Section 16.9)
- PK sampling (all subjects of study Part 1 and at least 12 subjects of study Part 2 and approximately 8 subjects of the MTD expansion cohorts with impaired renal function at baseline)
- Urine collection for PK analysis (to be performed in approximately 8 subjects in Part 1 or Part 2 MTD expansion cohorts, see Section 9.4.2.1)
- Dispense of study medication (BAY 1163877) and diary
- → Oral administration of BAY 1163877 (single dosing for subjects with PK assessment, twice daily dosing for subjects without PK assessment and for subject in Part 3)
- → Oral administration of a single dose of BAY 1163877 after at least 8 hours of overnight fast as specified in Section 8.4.2.2.1 ("food effect assessment" only)
- Toxicities / AE assessment and recording (if applicable)

 Modified by Amendment 7, see section 15.6.2.22

 Part 3 added by Amendment 7, see section 15.6.2.22

No. BAY 1163877 / 16443

17 Oct 2018 Version 8.0 Page: 76 of 395

#### Day 2

No administration of BAY 1163877 ("drug-free day") for subjects with PK assessment (all subjects of study Part 1 and at least 12 subjects with PK assessment in study Part 2 and approximately 8 subjects with PK assessment in the MTD expansion cohorts with impaired renal function at baseline [including "food effect assessment"])

- Twice daily administration of BAY 1163877 for subjects without PK assessment (remaining subjects of study Part 2) and for subjects of Part 3
- Update of concomitant therapy
- Physical examination
- Ask subject for changes in vision
- Cardiovascular assessment (BP and HR)
- Measurement of body temperature
- Single ECG reading (see Section 9.5.3.4)
- ECOG performance status
- PK sampling (all subjects of study Part 1 and at least 12 subjects of study Part 2 and approximately 8 subjects of the MTD expansion cohorts with impaired renal function at baseline) 
- Toxicities / AE assessment and recording (if applicable)

#### Day 3

- Update of concomitant therapy
- Physical examination
- Ask subject for changes in vision
- Cardiovascular assessment (BP and HR)
- Measurement of body temperature
- ECOG performance status
- Only for subjects included in study Part 1/ dose escalation (all comer): Blood (serum) samples collection for biomarker investigations, see Table 16-5
- PK sampling (all subjects of study Part 1 and at least 12 subjects of study Part 2 and approximately 8 subjects of the MTD expansion cohorts with impaired renal function

 Modified by Amendment 7, see section 15.6.2.22

<sup>64 Part 3 added by Amendment 7, see section 15.6.2.22

 Modified by Amendment 7, see section 15.6.2.22

17 Oct 2018 Version 8.0 Page: 77 of 395

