#### Targeted / planned enrollment:

- Study Part 1 / dose escalation (all comer): The total number of subjects will depend on the number of cohorts necessary to identify the MTD. Relative bioavailability of the tablet formulation in comparison to the solution formulation will be performed in all subjects enrolled in one of the dose escalation cohorts; pharmacokinetic data are needed in a minimum of 3 subjects for relative bioavailability assessment.
- Study Part 1 / MTD expansion (all comer): Additional subjects will be enrolled to have 20 evaluable "all comer" subjects treated at MTD.
- Study Part 2 / MTD expansion (sqNSCLC + LAC + BC + SCCHN): additional subjects will be enrolled to have 20 evaluable subjects with sqNSCLC or LAC and at least 30, up to a maximum of 50 evaluable subjects with BC and at least 8 subjects with SCCHN treated at MTD. 
- Study Part 3 / MTD expansion "Safety cohort" (sqNSCLC + LAC + BC): additional subjects will be enrolled to have approximately 20 subjects with sqNSCLC or LAC and approximately 20 subjects with BC treated at MTD.

PK assessments will be performed in all subjects participating in study Part 1 / dose escalation and MTD expansion (all comer) and study Part 3/ MTD expansion "Safety cohort". Additionally, PK assessments are planned in at least 12 subjects participating in study Part 2 / MTD expansion (sqNSCLC + LAC + BC + SCCHN) such that valid PK data are available in 8 subjects and in approximately 8 subjects of the MTD expansion cohorts with impaired renal function at baseline. Food effect PK assessment is planned in approximately 8 subjects enrolled in the MTD expansion cohorts (study Part 1 and Part 2). Subjects participating in "food effect assessment" in study Part 2 may be included in the total sample size of 12 if all protocol requirements are met.

All subjects participating in either of the 3 MTD expansion cohorts (Part 1, Part 2 and Part 3 despite subjects with impaired renal function) will have 2 PK samples drawn for the purpose of exposure-response modelling on Day 1 of Cycles 2, 3, 4, and 5 (1 blood sample just before the morning dose of BAY 1163877 and 1 blood sample between 0.5 and 1.5 hours post-dose). Subjects in Part 3 will provide one PK sample within 1 hour of biopsy collection in Cycle 2. The dose needs to be taken under supervision and the time

 Part 3 - Safety cohort - was added by Amendment 7, see section 15.6.2.6

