When a subject starts new anti-cancer therapy, he / she is no longer considered "on study". An End of Treatment (EOT) visit will be performed for all subjects within 0-14 days after

<sup>32 Part 3 - Safety cohort - was added by Amendment 7, see section 15.6.2.6

17 Oct 2018 Version 8.0 Page: 40 of 395

administration of the last dose of BAY 1163877. The Follow-up visit for subjects who either discontinue prematurely or finish dosing with BAY 1163877 will be performed 30-35 days after the last study drug treatment. There will be no long-term (survival) follow-up (FU) period.

Treatment: Subjects with PK assessment (all subjects of study Part 1 and 3 and at least 12 subjects of study Part 2 and approximately 8 subjects of the MTD expansion cohorts with impaired renal function at baseline) will receive BAY 1163877 (tablet or solution) on a continuous schedule starting with single-dose administration on Cycle 1, Day 1, followed by a "drug-free day" (to enable single dose PK assessments, except for subjects in Part 3 who will receive BAY 1163877 twice daily continuously with no "drug free day"). Treatment with BAY 1163877 will resume on Day 3 of Cycle 1 if no protocoldefined dose-limiting toxicities (DLTs) are reported. Starting on Cycle 1, Day 3, the study drug will be self-administered twice daily for the remaining 19 days of Cycle 1. For subsequent cycles, study drug will be administered twice daily for 21 days until disease progression or as long as clinical benefit is assumed by the investigator or until unacceptable toxicity occurs.

In one of the dose escalation cohorts in study Part 1 ("tablet bridging cohort"), relative bioavailability of the tablet formulation will be assessed by administration of a single dose of the tablet formulation on Cycle 1, Day -3. Starting with Cycle 1, Day 1, subjects enrolled in the "tablet bridging cohort" will continue with the solution formulation as described above. Depending on the results from the relative bioavailability assessment, subjects who initially start with solution formulation may be switched to tablet formulation in later cycles.

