If the dose escalation stops, the sample size for the MTD cohort will be expanded up to a total of 20 evaluable subjects (study Part 1 / MTD expansion cohort (all comer)).

No intra-subject dose escalation is permitted. Dose interruptions and / or dose reductions may be required based on individual safety and tolerability.

**Pharmacokinetics (PK):** Single- and multiple-dose PK of BAY 1163877 will be evaluated in plasma samples collected on Cycle 1, Day -3 in the "tablet bridging cohort", and on Cycle 1, Days 1 and 15 in all subjects participating in Part 1 (all comer) and in at least 12 subjects participating in Part 2 (sqNSCLC + LAC + BC + SCCHN). In approximately 8 subjects enrolled in the MTD expansion cohorts (study Part 1 and Part 2), the effect of food on the PK of BAY 1163877 will be determined by comparing exposures on Cycle 1 Day -3 (administration after consumption of a high-fat, high-calorie breakfast) and Cycle 1 Day 1 (administration after an overnight fast of at least 8 hours), see Section 8.1. In the MTD expansion cohorts, in approximately 8 subjects with moderately impaired renal function at baseline (glomerular filtration rate [GFR] of 30 to 59 mL/min/1.73 m^2 according to the modified diet in renal disease [MDRD] abbreviated formula), serial PK blood samples will be collected on Cycle 1 Day 1 and Day 15. In all

17 Oct 2018 Version 8.0 Page: 43 of 395

subjects participating in Study Part 3/"Safety cohort", multiple dose PK of BAY 1163877 will be evaluated in plasma samples collected on Cycle 1, Day 15.34

Plasma concentration of BAY 1163877 will be measured using a validated method.

In approximately 8 subjects enrolled in MTD expansion cohorts (study Part 1 and Part 2), urine will be collected for 24 hours after dosing on Cycle 1, Day 1 (concurrently with plasma PK samples) and analyzed using validated method.

Exploratory monitoring of metabolites may also be performed in pooled plasma samples (most likely at the MTD or the therapeutic dose) and urine samples.

The time points for PK sampling and further details are provided in Section 9.4.2.1.

Safety / tolerability: Drug safety will be monitored and evaluated continuously throughout the study, including a 30-day follow up period (time window +5 days) after administration of the last dose of BAY 1163877.

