(only for Study Part 3 / MTD expansion "Safety cohort" (sqNSCLC + LAC + BC)) 43

- Male or female subjects ≥18 years of age
- Life expectancy of at least 3 months
- Recovery to National Cancer Institute's Common Terminology Criteria for Adverse Events, version 4.03 (CTCAE v4.03) Grade 0 or 1 level or recovery to baseline preceding the prior treatment from any previous drug / procedure-related toxicity (subjects with persistent alopecia, anemia, and / or hypothyroidism can be included).

 Part 3 was added by Amendment 7, see section 15.6.2.9

 Amended by Amendment 7, see section 15.6.2.9

 Part 3 - Safety cohort - was added by Amendment 7, see section 15.6.2.9

No. BAY 1163877 / 16443

[figure not shown]

17 Oct 2018 Version 8.0 Page: 49 of 395

- Eastern Cooperative Oncology Group (ECOG) Performance Status of 0, 1 or 2
- Adequate bone marrow, liver and renal function as assessed by the following laboratory requirements conducted within 7 days of starting the study treatment:
  - Absolute neutrophil count (ANC)  $\geq 1,500/\text{mm}^3$
  - Platelet count  $\geq 75,000/\text{mm}^3$
  - Total bilirubin ≤ 1.5 times the upper limit of normal (ULN). Documented Gilbert syndrome is allowed if total bilirubin is mildly elevated (< 6 mg/dL).
  - Alanine aminotransferase (ALT) and aspartate aminotransferase (AST)  $\leq$  2.5 x ULN ( $\leq$  5 x ULN for subjects with liver involvement of their cancer)
  - Alkaline phosphatase limit  $\leq 2.5$  x ULN ( $\leq 5$  x ULN for subjects with liver involvement of their cancer)
  - Lipase  $\leq 5 \times ULN$
  - Not more than Child-Pugh score B7 hepatic impairment
  - Glomerular filtration rate (GFR) ≥ 30 mL/min/1.73 m^2 according to the modified diet in renal disease (MDRD) abbreviated formula
- International normalized ratio (INR)  $\leq$  1.5 x ULN and partial thromboplastin time (PTT) or activated partial thromboplastin time (aPTT)  $\leq$  1.5 x ULN. Subjects being treated with anticoagulant, e.g. warfarin or heparin, will be allowed to participate provided no prior evidence of an underlying abnormality in these parameters exists. Close monitoring of at least weekly evaluations will be performed until INR is stable based on a pre-dose measurement as defined by the local standard of care.
- Subjects with a history of hypertension should be on stable anti-hypertensive medicine for more than 7 days before start of study treatment.

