#### 9.4.2 Pharmacokinetics

### 9.4.2.1 Drug measurements - amended

Pharmacokinetics of BAY 1163877 will be evaluated on Cycle 1, Day -3 ("tablet bridging cohort" and "food effect assessment", only), on Cycle 1, Day 1 after single-dose administration, and on Cycle 1, Day 15 after multiple-dose administration of BAY 1163877 at the respective dose level achieved during dose escalation.

Pharmacokinetic assessments will be performed in all subjects enrolled in Part 1 (dose escalation and MTD expansion (all comer) cohorts). The plan is to perform pharmacokinetic assessments in at least 12 subjects in Part 2 MTD expansion cohort (sqNSCLC + LAC + BC + SCCHN) such that valid PK data are available in 8 subjects. "Food effect assessment" will be performed in approximately 8 subjects enrolled in the MTD expansion cohorts (study Part 1 and Part 2). In the MTD expansion cohorts pharmacokinetic assessments will be performed in approximately 8 subjects with moderately impaired renal function at baseline (glomerular filtration rate [GFR] of 30 to 59 mL/min/1.73 m² according to the modified diet in renal disease [MDRD] abbreviated

 Whole section - immune priming - was added by Amendment 7, see section 15.6.2.24

77 Oct 2018 Version 8.0 Page: 87 of 395

formula). In all subjects participating in study Part 3/ MTD expansion "Safety cohort", multiple dose pharmacokinetics (on Cycle 1 Day 15) will be performed.

**Blood (plasma) samples for PK assessment of BAY 1163877** will be collected at the following time points:

- Cycle 1, Day -3 ("tablet bridging cohort" and "food effect assessment" only): single-dose PK
  - pre-dose and 0.5, 1, 2, 3, 4, 6, 8, 12, 24 and 48 hour(s) post-dose
- Cycle 1, Day 1: single-dose PK
  - pre-dose and 0.5, 1, 2, 3, 4, 6, 8, 12, 24 and 48 hour(s) post-dose (48-hours sample before administration of morning dose on Day 3)
- Cycle 1, Day 15: multiple-dose PK
  - pre-dose (before morning dose), and 0.5, 1, 2, 3, 4, 6, 8 and 12 hours post-dose (12-hours sample before administration of evening dose)
- Cycles 2-5, Day 1: exposure-response modeling (not in subjects with impaired renal function)
- pre-dose (before supervised dose administration), and 1 ( $\pm$  0.5) hour post-dose
- Cycle 2: Subjects in Part 3/ MTD expansion "Safety cohort" will provide one PK sample within 1 hour of biopsy collection in Cycle 2.

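### Renally impaired Part 3 subjects get two opposite Day 2 dosing instructions, and the 48-hour single-dose PK sampling is not limited to subjects who have a drug-free day

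*Protocol*

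**What the plan says.** **Who is in the renal PK group.** Section 6 (Pharmacokinetics) takes about 8 subjects with GFR 30-59 from the MTD expansion cohorts and says that "serial PK blood samples will be collected on Cycle 1 Day 1 and Day 15". Part 3 is one of these cohorts: the enrolment text of Section 6 speaks of "All subjects participating in either of the 3 MTD expansion cohorts (Part 1, Part 2 and Part 3 despite subjects with impaired renal function", where the word before the renal subjects evidently means except. Eligibility in Section 7.1.1.2 applies to every part: "Glomerular filtration rate (GFR) ≥ 30 mL/min/1.73 m 2 according to the modified diet in renal disease (MDRD) abbreviated formula". The food-effect and urine substudies are expressly limited to Parts 1 and 2; the renal group is not.

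**Dosing.** In Section 9.1.2.3.1, Day 2, the subjects who receive no drug include "approximately 8 subjects with PK assessment in the MTD expansion cohorts with impaired renal function at baseline". The next line orders "Twice daily administration of BAY 1163877 for subjects without PK assessment (remaining subjects of study Part 2) and for subjects of Part 3". Neither line yields to the other. Elsewhere Part 3 is on continuous dosing:
- Section 9.1.2.3.1, Day 1: "single dosing for subjects with PK assessment, twice daily dosing for subjects without PK assessment and for subject in Part 3".
- Section 6 (Treatment) lists the PK subjects, names the renal group among them, and adds "except for subjects in Part 3 who will receive BAY 1163877 twice daily continuously", with no drug-free day.
- Section 8.4.2.1 has Part 3 on twice-daily drug from Cycle 1 Day 1.
- Section 8.7 reserves the Cycle 1 PK dose count for Parts 1 and 2.

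**Sampling.** Section 9.1.2.3.1 lists PK sampling on Days 1, 2 and 3 for the renal group of the expansion cohorts, without excluding Part 3. Section 9.4.2.1 labels the Cycle 1 Day 1 series as single-dose and runs it to 48 h ("48-hours sample before administration of morning dose on Day 3"). For Part 3 as a whole, the same section describes only a multiple-dose profile on Day 15.

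**The concern.** A site with a renally impaired Part 3 subject cannot follow both Day 2 lines. If it follows the Part 3 dosing text, it is still told to collect a 48 h series that the protocol treats as a single-dose profile. AUC(0-tlast) and AUC are primary PK parameters (Section 9.4.2.2), and both presume that only one dose was given in the window.

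The renal group is there to show exposure in moderate impairment, the GFR range for which Section 9.1.2.3 asks for careful monitoring. If profiles that span several doses were listed or pooled beside true single-dose profiles from Parts 1 and 2, exposure would look raised for a reason unrelated to renal function. In a group of about 8, a few such profiles could shift the summary.

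**Working it through.** **1. The plan's own figures: which schedule is Part 3 on?** Section 8.7 sets 80% compliance in Cycle 1 at 32 doses with PK assessment (Parts 1 and 2 only) and 34 doses otherwise (including Part 3).
- Drug-free-day schedule: 1 + 2 × 19 = 39 doses; 0.8 × 39 = 31.2, rounded up to 32.
- Twice daily from Day 1: 2 × 21 = 42 doses; 0.8 × 42 = 33.6, rounded up to 34.

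Both figures reproduce, and they place Part 3 on the schedule with no drug-free day.

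**2. Doses inside the 48 h window.** With a drug-free day there is one dose, at 0 h. On twice-daily dosing there are four, at 0, 12, 24 and 36 h. The 24 h sample then follows two doses (if drawn before the Day 2 morning dose), and the 48 h sample follows four.

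**3. Size of the distortion.** The protocol gives neither half-life nor absorption rate, so both are assumed: half-life 3-24 h, ka 0.5-3/h. The model is one-compartment with first-order absorption, and per unit dose and volume

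C(t) = ka/(ka − ke) × [exp(−ke·t) − exp(−ka·t)], with ke = ln 2 / half-life.

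Twice-daily dosing is the sum of this curve started at 0, 12, 24 and 36 h. Sampling times are those of Section 9.4.2.1: 0, 0.5, 1, 2, 3, 4, 6, 8, 12, 24 and 48 h.

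*Worked case, half-life 12 h, ka 1/h:*
- Single dose: C(12) = 0.531, C(24) = 0.265, C(48) = 0.066.
- Twice daily: C(12) = 0.531; C(24) = 0.265 + 0.531 = 0.796; C(48) = 0.066 + 0.133 + 0.265 + 0.531 = 0.995.
- Linear trapezoid, 12-48 h, single dose: 12 × (0.531 + 0.265)/2 + 24 × (0.265 + 0.066)/2 = 8.75.
- Linear trapezoid, 12-48 h, twice daily: 12 × (0.531 + 0.796)/2 + 24 × (0.796 + 0.995)/2 = 29.45.
- Area 0-12 h is about 8.1 in both, so the ratio is (8.1 + 29.45)/(8.1 + 8.75) = 2.23.

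*Range, sampled AUC(0-48), twice daily over single dose, linear trapezoid:*
- ka 1.5/h: 1.73, 2.12, 2.20, 2.23 and 2.23 for half-lives of 4, 8, 12, 16 and 24 h.
- All of ka 0.5-3/h and half-life 3-24 h: 1.46 to 2.31.

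The linear-up/log-down rule gives slightly higher values: 1.64, 2.18, 2.33 and 2.28 at ka 1/h for half-lives of 3, 6, 12 and 24 h, and up to 2.4 at ka 0.5/h.

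**4. Terminal slope.** Under twice-daily dosing the 12, 24 and 48 h concentrations do not decline in any case tried (0.531, 0.796, 0.995 above). No terminal half-life can be fitted over 12-48 h. Section 9.4.2.2 makes AUC to infinity depend on half-life.

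**5. What survives.** Up to 12 h the two schedules give identical concentrations if the 12 h sample is drawn before the evening dose. The AUC(0-12) ratio is 1.00, Cmax over 0-12 h is unchanged, and a 6-12 h slope can still be fitted. Section 9.4.2.1 states that the 12 h sample precedes the evening dose for Day 15, but not for Day 1. The Day 15 profile is the same under either schedule.

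**The case against.** The strongest reply is that Part 3 dosing is already settled. Section 6 names the renal group and then excepts Part 3 in the same sentence; Sections 8.4.2.1 and 8.7 and the Day 1 line agree. Since Part 3 PK is otherwise described as Day 15 only, the renal single-dose profiles can be read as belonging to Parts 1 and 2, with a missing qualifier as a drafting lapse. **This largely stands.** A reader might infer from the Day 2 lines that Part 3 dosing is open throughout the protocol, and the other sections do not support that. But it does not remove the unqualified Day 2 line or the unqualified Day 1-3 sampling, which are the lists a site works from.

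A second reply is that the harm is conditional. Some of the 8 must enter Part 3, be dosed twice daily, be sampled to 48 h, and be analysed as if single-dosed. Sections 9.4.2.1 and 9.4.2.2 use actual times relative to dosing and restrict analysis to valid PK data, and Section 10.4.5 specifies no renal comparison. **This stands too.** A reader might infer that the trial will report a false rise in renal exposure, but no such analysis is laid down and all inference is exploratory. A reader might also infer that the whole Day 1 profile is void; Cmax and AUC(0-12) are not.

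Finally, the Section 16.1 flow charts were not in the text available here, and their footnotes may separate Part 3. Sections 9.1.2.3.1 and 9.4.2.1 would still need to match them.

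**Conclusion.** The point holds as an internal inconsistency with a conditional PK consequence. For renally impaired Part 3 subjects, the Day 2 list contradicts itself, and the sampling text asks for a single-dose profile that the Part 3 dosing text does not allow. If such a subject is dosed twice daily, AUC(0-tlast) as sampled is inflated roughly 1.5 to 2.3 times, and the 12-48 h half-life and the AUC to infinity that rests on it are lost. Those factors depend on a one-compartment model and on assumed ka and half-life. Under the drug-free-day reading the profile is valid. The number affected, some of about 8, is not stated. No view is taken here on which schedule is right.

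**What to change.** 1. Reconcile Section 6 (enrolment, Treatment and Pharmacokinetics paragraphs), Section 8.4.2.1, Section 9.1.2.3.1 (Days 1, 2 and 3) and Section 9.4.2.1 on dosing and Day 1-3 PK sampling for renally impaired Part 3 subjects, and check the flow charts against the result. The choice of schedule is the sponsor's.
2. State that, for any subject not on the single-dose schedule with a drug-free day, only Cmax and AUC(0-12) are derived from Day 1, with the 12 h sample drawn before the evening dose.
3. State that AUC, AUC(0-tlast) and half-life from such a profile are neither reported nor pooled as single-dose parameters.
4. Base any comparison of renal exposure across parts on Cmax, AUC(0-12) and the Day 15 AUC(0-12)md, which are available under either schedule.

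The cost is protocol wording. The downside is that subjects dosed twice daily from Day 1 contribute no single-dose half-life or AUC to infinity.
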